as a biological variable will be considered in all analyses. Statistical Analyses. The effect of opioid taper on changes in pain responses (CPT, QST), and functional outcomes (PROMIS domains) over time will be examined using longitudinal mixed-effects regression modeling, using general linear regression modeling with regularization as a function of baseline dose, end dose, and taper rate. These longitudinal profiles will be examined using a linear mixed effects framework with SAS Proc Mixed in which all available data collected during follow-up are used. Mixed models can account for the correlation between repeated measures and handle non-excessive missing data better than traditional models and allow for use of time-independent and time-dependent covariates. To assess patterns of attrition over time, a comparison of withdrawal rates and time to withdrawal will be included. Separate mixed effects regression models will be generated for each of the continuous outcome measures of interest (pain responses, functional outcomes). Random slopes and intercepts will be modeled to represent the participant-level deviation from the fixed-effect slope over time and intercept, respectively. Restricted maximum likelihood estimation will be used and the most appropriate covariance structure examined. Scores will be analyzed as repeated observations of the dependent variable, with mean-centered baseline outcome scores serving as a covariate. Other predictor variables will include baseline demographic characteristics of the patient, severity and chronicity of pain suffered, and opioid use history. Baseline measures will be analyzed as time-independent covariates. The Akaike information criterion will be used to evaluate overall model fit and to select the best-fitting longitudinal change pattern. .

The following documents are currently attached to this item:

There are no documents attached for this item.

Data confidentiality

- x Paper-based records will be kept in a secure location and only be accessible to personnel involved in the study.**
- x Computer-based files will only be made available to personnel involved in the study through the use of access privileges and passwords.**
- x Prior to access to any study-related information, personnel will be required to sign statements agreeing to protect the security and confidentiality of identifiable information.**
- x Wherever feasible, identifiers will be removed from study-related information.**

A Certificate of Confidentiality will be obtained, because the research could place the subject at risk of criminal or civil liability or cause damage to the subject's financial standing, employability, or liability.

A waiver of documentation of consent is being requested, because the only link between the subject and the study would be the consent document and the primary risk is a breach of confidentiality. (This is not an option for FDA-regulated research.)

Precautions are in place to ensure the data is secure by using passwords and encryption, because the research involves web-based surveys.

Audio and/or video recordings will be transcribed and then destroyed to eliminate audible identification of subjects.

Subject Confidentiality

All records will be kept strictly confidential. No one except the researchers will know the subjects are in a research study. Data forms for the collection of health and study data will be coded with each subjects unique identification number. No data form will identify the participants by name. Hardcopies of data forms will be kept in locked files with keys held only by the study investigator. No presentation or publication of the results of this study will refer to the individual participants or present information that would identify any participant. All persons working on the proposed work will have completed HIPAA training and the Collaborative Institutional Training Initiative (CITI) Basic Courses in the Protection of Human Research Subjects and Biomedical Focus Responsible Conduct of Research (RCR) modules.

Sensitive Research Information*

Does this research involve collection of sensitive information about the subjects that should be excluded from the electronic medical record?

No

Subject Privacy

Privacy refers to the person's desire to control access of others to themselves. Privacy concerns people, whereas confidentiality concerns data. Describe the strategies to protect privacy giving consideration to the following: The degree to which privacy can be expected in the proposed research and the safeguards that will be put into place to respect those boundaries. The methods used to identify and contact potential participants. The settings in which an individual will be interacting with an investigator. The privacy guidelines developed by relevant professions, professional associations and scholarly disciplines (e.g., psychiatry, genetic counseling, oral history, anthropology, psychology).

Privacy will be strictly maintained in all aspects of participation. Screening and testing sessions will take place in private rooms at the U Penn Pain Medicine Clinic where strict patient privacy is enforced and all staff are HIPAA certified.

Data Disclosure

Will the data be disclosed to anyone who is not listed under Personnel?

Study data will not be disclosed to anyone who is not listed under Study Personnel.

Data Protection*

- Name**
- Street address, city, county, precinct, zip code, and equivalent geocodes**
- All elements of dates (except year) for dates directly related to an individual and all ages over 89**
- Telephone and fax number**
 - Electronic mail addresses**
- Social security numbers**
- Medical record numbers**
 - Health plan ID numbers**
 - Account numbers**
 - Certificate/license numbers**
 - Vehicle identifiers and serial numbers, including license plate numbers**
 - Device identifiers/serial numbers**
 - Web addresses (URLs)**
 - Internet IP addresses**
 - Biometric identifiers, incl. finger and voice prints**
 - Full face photographic images and any comparable images**
 - Any other unique identifying number, characteristic, or code**
- None**

Does your research request both a waiver of HIPAA authorization for collection of patient information and involve providing Protected Health Information ("PHI") that is classified as a "limited data set" (city/town/state/zip code, dates except year, ages less than 90 or aggregate report for over 90) to a recipient outside of the University of Pennsylvania covered entity?

No

Tissue Specimens Obtained as Part of Research*

Are Tissue Specimens being obtained for research?

No

Tissue Specimens - Collected during regular care*

Will tissue specimens be collected during regular clinical care (for treatment or diagnosis)?

No

Tissue Specimens - otherwise discarded*

Would specimens otherwise be discarded?

No

Tissue Specimens - publicly available*

Will tissue specimens be publicly available?

No

Tissue Specimens - Collected as part of research protocol*

Will tissue specimens be collected as part of the research protocol?

No

Tissue Specimens - Banking of blood, tissue etc. for future use*

Does research involve banking of blood, tissue, etc. for future use?

No

Genetic testing

If genetic testing is involved, describe the nature of the tests, including if the testing is predictive or exploratory in nature. If predictive, please describe plan for disclosing results to subjects and provision of genetic counseling. Describe how subject confidentiality will be protected Note: If no genetic testing is to be obtained, write: "Not applicable."

Not applicable

Consent

1. Consent Process

Overview

After expressing interest in the study to the co-investigator study physician, the project manager will meet with the prospective participant in a private office to review the consent document as well as provide an oral explanation of the study. Individuals will be given a chance to ask questions before making a considered decision about whether or not to participate in the study. Via the consent process, prospective subjects will be reminded that their participation in this study is entirely voluntary, and that they should carefully read the information in the consent, and ask questions about anything not understood, before deciding whether or not to participate. It will be emphasized that they have the right to refuse to participate in this study, and if they choose not to participate, it will not affect their relationship with the University and their right to health care or other services otherwise entitled. Prospective subjects will also be informed that if they decide to participate, they are free to withdraw consent and discontinue participation at any time without prejudice to future care at the University of Pennsylvania. As stipulated in the consent form, subjects may withdraw consent at any time and discontinue participation without penalty. No legal claims, rights or remedies are waived as a result of their participation in this research study. Consent will be obtained by the study physician.

Children and Adolescents

Not applicable

Adult Subjects Not Competent to Give Consent

Not applicable

2. Waiver of Consent

Waiver or Alteration of Informed Consent*

No Waiver Requested

Minimal Risk***Impact on Subject Rights and Welfare***

Waiver Essential to Research*

Additional Information to Subjects

Written Statement of Research*

No

If no written statement will be provided, please provide justification

The following documents are currently attached to this item:

There are no documents attached for this item.

Risk / Benefit

Potential Study Risks

Cold-Pressor Pain Induction (CP): As it will induce acute pain, the cold-pressor (CP) procedure will cause the subject discomfort. Subjects will be assured via the consent process that they may discontinue their study participation at any time if they decide not to undergo the painful experience. The PI has performed these pain induction techniques on close to 200 subjects in past research endeavors without a single adverse event. Throughout the pain procedures, vital signs will be continuously monitored and staff available to communicate any discomforts they may experience. Potential CP risks to the subjects are minimal; injury including tissue damage is unlikely as exposure time is to be short (5min); the subject can remove the hand from the ice water should it become subjectively intolerable and all trials will be truncated at 300 seconds. No adverse effects have been reported with the CP pain induction technique in over 75 years of published research. Quantitative sensory testing Pain Induction (QST): Like the cold-pressor procedure, the QST is designed to induce acute pain, thus will cause the subject discomfort. Subjects will be assured via the consent process that they may discontinue their study participation at any time if they decide not to undergo the painful experience. Vital signs will be measured before and after the test, and study staff available to communicate any discomforts they may experience. The heat devices are designed not to exceed safe temperatures and have automatic shut-off. Potential risks to the subjects are minimal, which include a burn such as a bad sunburn. These happen very infrequently (1%). Breach of Confidentiality: Participation in this study may constitute a social risk to the participant in that others may learn that he or she takes opioids regularly for chronic pain. Due to the sensitive nature of this information, privacy and confidentiality will be strictly maintained in all aspects of participation. Testing sessions will take place in private rooms where strict privacy is enforced and all research and clinical staff are HIPAA certified.

Potential Study Benefits

The potential benefit for both the participants and broader segments of society is to improve the management of chronic pain so as to improve outcomes in this challenging and growing patient population, including increases in functionality, satisfaction with treatment and quality of life. Better understanding of the pros and cons of opioid therapy for the treatment of chronic pain can guide clinical practice based upon evidence. Participants will be informed that, with the exception of study payment, no direct benefit is expected to accrue to them from participation in the study.

Alternatives to Participation (optional)

Data and Safety Monitoring

The Principal Investigator will have responsibility for monitoring the safety management of this trial, and comply with the reporting requirements. The PI will be responsible for monitoring the data to ensure safety of participants and will closely supervise the research staff by means of regularly scheduled weekly meetings to discuss interactions with the participants. Monitoring meetings will be conducted monthly with the investigative team throughout the study.

The following documents are currently attached to this item:

There are no documents attached for this item.

Risk / Benefit Assessment

Participants will be informed that, with the exception of study payment, no direct benefit is expected to accrue to them from participation in the study. Based on the characteristics of the risks associated with study participation, and efforts in place to minimize these risks, the risks to subjects are reasonable in relation to the anticipated benefits to research participants and others. The potential benefit of this study is expected to far outweigh any minimal risk by providing valuable information on the effects of opioid therapy on chronic pain and functionality.

General Attachments

The following documents are currently attached to this item:

Informed consent form (icfopioidtapertrackedchanges9.17.18pc.doc)

Questionnaires (promis-paininterference.pdf)

Questionnaires (cows.pdf)

Questionnaires (lansstool.pdf)

Questionnaires (stanfordexercisequestionnaire.pdf)

Grant Application ([name])

Informed consent form (icfopioidtaperfinal.doc)

Additional forms (references.docx)

Recruitment materials (recruitmentflyertaperstudy7.23.18sp.pdf)

Informed consent form (icfopioidtapercleancopy9.17.18pc.doc)

Cover Letter (responsestoirstipulations9.17.18pc.docx)

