The overall Specific Aim of this proposal is to determine the effect of opioid taper on pain sensitivity in patients with chronic pain. Specifically, in a well-characterized sample of men and women with chronic neuropathic pain and receiving high-dose opioid therapy (200mg morphine equivalents/day [MED]), experimental pain responses will be serially described over the course of an individualized opioid taper to a safer dose of 90mg MED for up to 12 months. Changes will be inspected within-subject over time, and pain perception will be measured with two valid and reliable experimental pain induction techniques commonly used to measure OIH (cold-pressor, quantitative sensory testing); in addition, related functional improvements and subject-level predictors of response will be described. Hypothesis 1. Subjects undergoing opioid taper will have improved pain responses over time compared to within-subject baseline as measured by cold-pressor and quantitative sensory pain testing. Hypothesis 2. Improvements in experimental pain responses will be positively related to improved functional outcomes compared to within-subject baseline as measured by the PROMIS physical, mental and social health measures. Hypothesis 3. Degree of improvement in experimental pain responses related to opioid taper will be predicted by demographic, pain, and opioid use history characteristics of the subject. Data showing that pain perception improves as opioids are withdrawn would provide an evidence-based, mechanistic rationale for opioid taper in patients with chronic pain and have the potential to support a sea-change in opioid prescription practices. In that ongoing opioid therapy brings with it significant health risks for the patient and the community, it is critical that empirical evidence of its efficacy be demonstrated to balance the benefits with the risks of adverse events, potential misuse and abuse, and patient safety.

Primary outcome variable(s)

The primary dependent variable, pain perception, will be measured using two highly reliable and valid pain induction techniques, the cold-pressor test (CPT) and quantitative sensory testing (QST), employing procedures consistent with those described in the literature. Order of pain testing will vary, and three aspects of the pain response will be captured at each study session: evoked pain; temporal summation; and conditioned pain modulation, which map on to the hypothesized peripheral, spinal and supra-spinal mechanisms of OIH.

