The study will be staff by a 55% FTE Project Director assisted by two part time graduate student research assistants (10hr/week) who will assist with pain testing and data collection. The project director is well-trained and experienced in all study procedures and human subjects research; with the PI, he will ensure the research assistants are trained and qualified to conduct research. Weekly research meetings between the investigators and study staff will occur to ensure staff are adequately informed about the protocol and their research-related duties. The PI has her own locking office space ([name], approximately 170 square feet). All faculty offices come equipped with locked filing cabinets, bookshelves, desk, minimum 4 GHz computer with HP printer, Windows XP service pack 3 operating system, Microsoft Office Professional (Word, Excel, PowerPoint, Access), SPSS or SAS statistical analysis software, and e-mail and internet access. With the same resources, an adjacent cubicle space is dedicated to the study research assistant. NHS copier, printer, fax and scanner facilities are available on each floor. Research visits will take place in a private office at the U Penn Pain Medicine clinic. The Penn Pain Medicine Center currently has eight clinical exam rooms, 7 administrative offices (office manager, physician, fellow, and resident offices), 5 support staff offices (2 billing/new patient coordinator, surgical coordinator, and research coordinator offices). There is a large clinical research area which houses the office of the clinical research coordinator along with 3 bays/exam locations for research patients. Study sessions will occur one of several small (10 ft x 15 ft) private examination rooms located onsite, complete with examining table, chair, bedside stand, desk, computer, and sink.

Characteristics of the Study Population

Target population

The sample will consist of 25 male and female adults with chronic neuropathic pain on opioid therapy and preparing to voluntarily undergo a prescribed opioid taper.

Subjects enrolled by Penn Researchers

25

Subjects enrolled by Collaborating Researchers

0

Accrual

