Participants will be recruited from those treated at the large and nationally-renowned Penn Pain Medicine Center at the University of Pennsylvania Penn Medicine Neuroscience Center. The Penn Pain Medicine Center provides interdisciplinary, multimodal pain care to over 12,000 outpatients annually, an estimated 20% of whom are taking opioids on a regular basis. At any one point in time an estimated 50 patients are undergoing opioid taper, up to half of whom are tapered from opioid doses greater or equal to 200mg MED. Due to anticipated rates of dropout, 25% oversampling for these individuals is planned. Results from previous studies have demonstrated moderate to large effect size estimates of opioids on cold-pressor and QST experimental pain responses. Based on these estimates, a sample size

of 25 will have over 99% power to detect differences in outcome. Using an alpha of 0.05/4 (Bonferroni correction) to account for multiple outcomes, we will have over 90% power to detect significant changes at the 0.01 level for all of the outcomes. Cross-sectional and prospective studies demonstrate statistically significant differences in experimental pain responses with changes between 80-90mg MED (10,11,70); since MED decreases in the proposed work will be 110 MED (tapers from 200MED to 90MED), we anticipate having no difficulty discerning taper effects on pain responses.

Key inclusion criteria

(1) between ages of 21-60; (2) documented chronic neuropathic non-malignant pain condition of at least one year duration; (3) on 200mg MED for at least 6 months; (4) have fully engaged in all prescribed non-opioid pain management treatments; (5) willing to undergo prescribed opioid taper; (6) otherwise in good physical and mental health, or in the care of a physician who is willing to take responsibility for such treatment; and (7) able to understand the purpose and instructions of the study, and provide informed consent as approved by the University of Pennsylvania IRB.

Key exclusion criteria

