Standard of Care: In light of the demonstrated health risks associated with daily opioid doses greater than 90mg MED, current practice at the Penn Pain Medicine Center is to taper all chronic pain patients down to or below this MED and to stabilize on the lowest effective dose as agreed upon by the patient and prescriber. The actual rate of taper varies with tolerability and availability of dosages of opioid, but averages 10-15% decrease/month. Final stabilization dose also varies between patients but the goal to achieve a daily dose of 90mg MED. Prior to attempting taper, an adequate trial of all non-opioid and non-pharmacologic interventions are provided so that the patients chronic pain is under maximal control. Research Purposes: Baseline Study Session: Study data collection will begin immediately following consent, with the collection of urine toxicology, chronic pain and opioid use history, and baseline pain testing (see attached Data Collection Schedule). It is expected that it will take 30min to complete the baseline measures and another 30min to perform the pain testing battery, totaling 60min for the first session; subsequent sessions should last no longer than 30min. Study Sessions. All data collection will take place in a private office located in the Penn Pain Medicine Center, with sessions scheduled within 3hrs of morning opioid dose, and subjects instructed to ingest no caffeine or nicotine for 1hr prior to each session. Concurrent medication use since last visit, and last menstrual period date for female participants will be documented. A withdrawal score and urine sample for toxicology will be collected immediately prior to pain testing to verify compliance with opioid treatment. Sessions will be scheduled to coincide with regular clinic visits as possible. All study data will be collected using REDCap (Research Electronic Data Capture), utilizing PhenX data collection tools as available. Pain Responses: The primary dependent variable, pain, will be measured using two highly reliable and valid pain induction techniques, the CPT and QST, employing procedures consistent with those described in the literature. Order of pain testing will vary, and three aspects of the pain response will be captured at each study session: evoked pain; temporal summation; and conditioned pain modulation, which map on to the hypothesized peripheral, spinal and supra-spinal mechanisms of OIH. Protocols for each assay have been uploaded. Evoked pain perception: The CPT apparatus consists of a circulating water bath maintained at $1^{\circ}\text{C} \pm 0.5^{\circ}\text{C}$, into which subjects immerse their dominant hand and forearm to elicit a nociceptive response. Elapsed time until pain threshold and tolerance are reached measures evoked pain. A stopwatch is simultaneously activated with arm immersion, and subjects instructed to indicate when the cold sensation becomes a painful sensation (pain threshold), and when the pain becomes subjectively intolerable or spontaneous hand removal (pain tolerance). Immediately after hand withdrawal, subjects are asked to mark maximal pain intensity on a computerized visual analogue scale (Co-VAS, 0-100). Temporal Summation (TS): As a component of QST, a thermal testing analyzer (TSA; Medoc TSA-2001 device) with a sized 30 x 30 mm Peltier thermode, is used for the assessment

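### Both power figures are quoted at the full enrolment of 25 although dropout is anticipated, and the adjusted alpha appears as both 0.05/4 and 0.01

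*Combined protocol and SAP*

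**What the plan says.** Target population (Characteristics of the Study Population) fixes the size: "The sample will consist of 25 male and female adults with chronic neuropathic pain on opioid therapy". The entries that follow it give 25 enrolled by Penn researchers and 0 by collaborators.

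Accrual then makes these statements in one paragraph:

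- On loss: "Due to anticipated rates of dropout, 25% oversampling for these individuals is planned". No dropout rate is given.
- On the effect: "Results from previous studies have demonstrated moderate to large effect size estimates of opioids on cold-pressor and QST experimental pain responses". No number is attached.
- On power: a sample size "of 25 will have over 99% power to detect differences in outcome". No alpha is attached to this figure.
- On multiplicity: "Using an alpha of 0.05/4 (Bonferroni correction) to account for multiple outcomes", followed directly by "we will have over 90% power to detect significant changes at the 0.01 level for all of the outcomes".

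Primary outcome variable(s) says that "three aspects of the pain response will be captured at each study session: evoked pain; temporal summation; and conditioned pain modulation". Under Procedures, the first of these is split: "Elapsed time until pain threshold and tolerance are reached measures evoked pain". A maximal-intensity rating is also taken after hand withdrawal. The Analysis Plan specifies a linear mixed model with random intercepts and slopes using all available follow-up data, and a comparison of withdrawal rates. It states no alpha and no list of primary measures.

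**The concern.** Oversampling for dropout means that the enrolled number exceeds the number the calculation needs. Here the two are the same. Either the 25 already contains the oversampling, so that about 20 evaluable participants are expected and power is overstated for them, or the 25 is the evaluable target and the enrolment entry omits the oversampling. The enrolment fields favour the first reading but do not settle it.

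The alpha has a similar problem. A divisor of 4 gives 0.0125, while 0.01 is what a divisor of 5 would give. The outcome text names three aspects of the pain response. Depending on how evoked pain is counted, the family has three, four or five members.

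A reader therefore cannot tell how many evaluable participants the power claim rests on, or which threshold decides significance for which measure. The second matters most at reporting, because an unnamed family leaves room to choose its members after the results are seen.

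**Working it through.** **Inputs from the documents.** N = 25 (Target population, Accrual); 25% oversampling, power over 99% and over 90%, alpha 0.05/4 and 0.01 (Accrual); within-subject change from baseline (Design).

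**Assumptions, not in the documents.** A paired t test on within-subject change as a simple stand-in for the mixed model; alpha 0.05 for the 99% figure; two-sided unless stated. d_z is the mean change divided by the SD of the change.

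**1. Can the plan's figures be reproduced?** No. The Accrual section gives no numeric effect, SD, correlation or sidedness. The 30 to 40 visits (Subject compensation) and the mixed model (Analysis Plan) are stated, but neither is tied to the power statement. The check below therefore starts from the plan's own claim and asks what effect it implies.

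**2. Sample size arithmetic.** 20 x 1.25 = 25. Alternatively 25 x 1.25 = 31.25, or 32 enrolled, which conflicts with the enrolment entry of 25 + 0.

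**3. Effect implied by the 99% claim.** Power = P(|T| > t_crit), where T is noncentral t with n - 1 degrees of freedom and noncentrality d_z x sqrt(n). Solving for 99% at n = 25 and alpha 0.05 gives d_z = 0.894 (noncentrality 0.894 x 5 = 4.47, t_crit = 2.064).

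**4. The same effect at smaller evaluable numbers.**

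| n | Noncentrality | Power at 0.05 | Power at 0.0125 | Power at 0.01 |
|---|---|---|---|---|
| 25 | 4.47 | 99.0% | 95.3% | 94.3% |
| 22 | 4.19 | 97.9% | 91.6% | just under 90% |
| 20 | 4.00 | 96.6% | 87.8% | 85.7% |

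The n = 22 row illustrates an effective number between 20 and 25 when dropouts contribute partial data.

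**5. One-sided version.** The effect that just gives 99% at n = 25 is now d_z = 0.818. At n = 20 it gives 97.0% at 0.05 and 87.9% at 0.0125, almost the same as the two-sided result.

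**6. How large the effect must be.** For both claims to hold with 20 completers (two-sided), d_z must be at least 1.012 (99% at 0.05), against 0.894 at 25. The ratio is 1.012/0.894 = 1.13, so about 13% larger. For 90% power at 0.0125 alone, d_z must be 0.81 at n = 25 and 0.92 at n = 20.

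**7. Range for a moderate to large effect.** Taking paired d from 0.5 to 0.8, a convention assumed here, two-sided:

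| n | Power at 0.05 | Power at 0.0125 |
|---|---|---|
| 25 | 67% to 97% | 44% to 89% |
| 20 | 56% to 92% | 33% to 78% |

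**8. Alpha.** 0.05/3 = 0.0167; 0.05/4 = 0.0125; 0.05/5 = 0.01. From the table in step 4, moving from 0.0125 to 0.01 costs 95.3 - 94.3 = 1.0 point at n = 25 and 87.8 - 85.7 = 2.1 points at n = 20.

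**The case against.** The strongest reply is that the plan does not use a completers-only test. The mixed model uses every available observation, so someone who leaves early still contributes, and repeated testing can raise precision above that of a single paired comparison. This stands. It makes the n = 20 row a worst case: at an effective 22 the 90% claim at 0.0125 survives (91.6%), although the 99% claim does not (97.9%).

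A second reply is that Hypothesis 1 is directional, so a one-sided test is natural. Holding d_z at 0.894 and switching to one-sided at n = 20 gives 98.6% and 93.1%, which rescues the 90% figure. But that compares a one-sided test with an effect calibrated to a two-sided one. Once the effect is recalibrated (step 5), the shortfall returns.

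A third reply is that this is described as an observational pilot and that 0.01 may simply be 0.0125 rounded. The rounding explanation is possible and the power cost is small. Pilot status does not remove the need for a numeric power claim to match its own sample size and alpha.

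A reader might go further and infer that the figures of over 99% and over 90% are false. The documents do not support that: with a standardised change of about 0.9 or more both hold at 25, and at about 1.01 or more both hold even with 20 completers. Nor do they establish that the 25 certainly includes the oversampling, or that visits and model are missing from the plan. A grant application is listed as an attachment and was not available, so the inputs may exist there.

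**Conclusion.** The point holds as an inconsistency in the stated figures. Power is quoted at the enrolled number in the same paragraph that anticipates dropout, and the adjusted alpha appears as both 0.0125 and 0.01. Its size depends on the unstated effect. If the effect only just justifies the 99% claim at 25, a completers-only analysis of 20 falls 2.4 points short of 99% and 2.2 points short of 90% at 0.0125; partial data would reduce both shortfalls. If the effect is at least about 13% larger, neither claim is affected. These results rest on a paired t test as a stand-in for the mixed model, 20 evaluable participants as implied by 20 x 1.25, and alpha 0.05 for the 99% figure.

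The alpha mismatch is minor in power terms. It matters more that the four measures are unnamed, since that leaves the decision rule open. The missing numeric inputs prevent the figures from being verified but do not show that they are wrong.

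**What to change.** Keep enrolment at 25, and have the sponsor confirm whether that number includes the 25% oversampling.

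- If it does, as the enrolment entry suggests, state the anticipated dropout rate and the expected evaluable number (about 20). Restate power, or the minimum detectable within-subject change, at that number under the planned mixed model. Give the effect, correlation, visits and sidedness used. As a reference value, a two-sided paired t test with 20 participants has 90% power at 0.0125 for d of about 0.92. Retain the over 99% and over 90% figures only if those inputs support them.
- If it does not, the Accrual text and the enrolment entry contradict each other and the sponsor must reconcile them.

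Use the single alpha 0.05/4 = 0.0125, delete the reference to the 0.01 level, name the four pain measures it covers (the sponsor's choice), and carry the same alpha and list into the Analysis Plan.

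On the favoured reading this is a change of wording with no extra patients. The cost is that the stated power may become less favourable.
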